- Patients receiving concomitant medications that are known to be strong or moderate inducers of cytochrome CYP2C9 enzyme and/or strong inducers of CYP3A, strong inhibitors of CYP2C9 and/or strong or moderate inhibitors of CYP3A and the treatment cannot be discontinued or switched to a different medication within 5 half-lives or 1 week (whichever is longer) prior to Day 1 and for the duration of the study.

- At screening, pre-malignant clonal cytopenias or clonal cytopenia of unknown significance (CCUS).
- History of ongoing, chronic, or major recurrent infectious disease, at the discretion of the Investigator, at the start of screening.
- Patients with suspected or proven immunocompromised state at screening.
- Use of any biologic drugs targeting the immune system within 26 weeks of Day 1.
- Major non-cardiac surgical or major endoscopic procedures within the past 6 months prior to the start of screening.
- Multi-vessel coronary artery bypass graft (CABG) surgery within the past 3 years prior to the start of screening.
- Planned coronary revascularization (percutaneous coronary intervention (PCI) or CABG) or any other major surgical procedure during the study (until End of Study (EOS)).
- Symptomatic Class IV heart failure (New York Heart Association [NYHA]) at the start of screening.
- Women of childbearing potential, defined as all women physiologically capable of becoming pregnant, **unless** they are using highly effective methods of contraception for at least 3 months prior to first drug administration (Day 1), during dosing and for 5 months after Day 1.

Treatment Groups:

Active treatment: DFV890 administered orally once daily (QD) at various doses (0 mg [matching placebo], 10 mg, 25 mg, 50 mg, 100 mg) over four dosing periods of approximately 3 weeks each, for a total of approximately 12 weeks of treatment or a single s.c.dose (CCI mg) of MAS825 or matching placebo. Randomized to one of five treatment sequences comprised of various doses of DFV890, or a single s.c. dose of MAS825, and/or placebo. Investigational study treatment dose adjustments and/or interruptions are not permitted.

[figure not shown]
Data Monitoring/Other Committee: No

Key words

Coronary heart disease, CHIP, inflammatory marker reduction, NLRP3 inflammasome inhibitor

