	Unforeseen use of medication expected to have a limited effect on the primary endpoints (i.e., any other prohibited medications)	Only the assessment immediately following the event will be excluded for the purpose of this estimand
New-onset febrile infection	Febrile infection around time of assessment (details to be provided in the statistical analysis plan)	Only the assessment immediately following the event will be excluded for the purpose of this estimand
Nonadherence to study treatment (DFV890 only)	Greater than 20% of missed daily doses within 3 weeks prior to an assessment	Only the assessment immediately following the event will be excluded for the purpose of this estimand
	Any missed dose within the 2 days prior to an assessment	Only the assessment immediately following the event will be excluded for the purpose of this estimand

The handling of each intercurrent event specified in [Table 3-2](#), with the exception of changes in SoC CVD prevention medication, reflects what is referred to as the hypothetical strategy, which aims to mimic a scenario in which the intercurrent event did not actually occur and all participants had adhered to the randomized treatment throughout the course of the study. To enable this strategy, data from various assessments taking place after the event will be excluded from the primary analysis, as described in the table. The exception to this is changes to SoC CVD prevention medication, which will be handled by a treatment policy strategy, in which any occurrence of the event is ignored and the subsequent data are included in the analysis.

Additional information on the handling of the intercurrent events in the primary analysis is described in [Section 9.3.3](#).

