6.5 Dose modification

Investigational or other study treatment dose adjustments and/or interruptions are not permitted.

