6.7 Treatment of overdose

In the event of an overdose, the Investigator/treating physician should:

- Contact the medical monitor immediately.
- Evaluate the participant to determine, in consultation with the medical monitor, whether study treatment should be interrupted or whether the dose should be reduced.
- Closely monitor the participant for any AE/SAE and laboratory abnormalities until DFV890 can no longer be detected systemically (at least 7 days).
- Obtain a plasma sample for PK analysis within 7-10 days from the date of the last dose of study treatment if requested by the medical monitor (determined on a case-by-case basis).
- Document the quantity of the excess dose as well as the duration of the overdose.

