6.8.2 Prohibited medication

Strong or moderate inhibitors of CYP3A and/or strong inhibitors of CYP2C9 are prohibited. Strong or moderate inducers of CYP2C9 and/or strong inducers of CYP3A or strong or moderate dual inhibitors of CYP2C9 / CYP3A are prohibited. For a detailed list, please see [Table 6-6](#) below (please note that the list may not be comprehensive).

Considering the DDI potential for DFV890, should a participant have an incidental and limited need for a prohibited medication to be taken within the restricted timeframe, Investigators should discuss the case with the sponsor. The administration of any prohibited concomitant medication may require the participant to be withdrawn or DFV890 treatment to be put on hold.

Use of the treatments displayed in the below table is prohibited approximately 5 half-lives or 1 week (whichever is longer) prior to Day 1 until the EOS as described in [Table 6-7](#).

Table 6-6 Prohibited drugs due to DDI with DFV890 (CYP3A and CYP2C9 modulators)

Category of interaction	Drug Names
Strong inhibitors of CYP3A	boceprevir, ceritinib, clarithromycin, cobicistat, conivaptan, danoprevir/ritonavir ¹ , elvitegravir/ritonavir ¹ , grapefruit juice ² , idelalisib, indinavir, indinavir/ritonavir ¹ , itraconazole, josamycin, ketoconazole, lopinavir/ritonavir ¹ , mibefradil, mifepristone, nefazodone, nelfinavir, ombitasvir/paritaprevir/dasabuvir/ritonavir (Viekira Pak) ¹ , posaconazole, ribociclib, ritonavir, saquinavir, saquinavir/ritonavir ¹ , telaprevir, telithromycin, tipranavir/ritonavir ¹ , troleandomycin, tucatinib, voriconazole
Moderate inhibitors of CYP3A	aprepitant, amprenavir, atazanavir, atazanavir/ritonavir ¹ , casopitant, cimetidine, ciprofloxacin, crizotinib, darunavir, darunavir/ritonavir ¹ , diltiazem, dronedarone, duvelisib, erythromycin, faldaprevir, fedratinib, fluconazole, grapefruit juice, imatinib, isavuconazole, istradefylline, lefamulin, letermovir, Magnolia vine (Schisandra sphenanthera) ³ , netupitant, nilotinib, ravuconazole, tofisopam, verapamil, voxelotor
Strong inhibitors of CYP2C9	miconazole, sulfaphenazole, tasisulam
Strong inducers of CYP2C9	None reported to date
Moderate inducers of CYP2C9	enzalutamide, rifampicin
Strong inducers of CYP3A	apalutamide, avasimibe, carbamazepine, enzalutamide, ivosidenib, lumacaftor, mitotane, phenobarbital, phenytoin, rifampicin, rifapentine, St. John's wort (Hypericum perforatum) ³

¹ Combination therapy

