10.5.1 Liver event and laboratory trigger definitions & follow-up requirements

Table 10-1 Liver event and laboratory trigger definitions

Definition/ threshold	
Liver laboratory triggers If ALT, AST and TBIL normal at baseline:	
 • ALT or AST > 5 × ULN • TBIL > 3 × ULN (in the absence of known Gilbert syndrome) • ALT or AST > 3 × ULN and INR > 1.5 • Potential Hy's Law cases (defined as ALT or AST > 3 × ULN and TBIL > 2 × ULN [mainly conjugated fraction] without notable increase in ALP to > 2 × ULN) • Any clinical event of jaundice (or equivalent term) • ALT or AST > 3 × ULN accompanied by (general) malaise, fatigue, abdominal pain, nausea, or vomiting, or rash with eosinophilia • Any AE potentially indicative of a liver toxicity
If ALT or AST abnormal at baseline:	
 • ALT or AST > 3x baseline or > 300 U/L (whichever occurs first)

Table 10-2 Follow up requirements for liver laboratory triggers - ALT, AST, TBL

	ALT	TBL	Liver Symptoms	Action
ALT increase without bilirubin increase:				
	If normal at baseline: ALT > 3 x ULN If elevated at baseline: ALT > 2 x baseline or > 300 U/L (whichever occurs first)	Normal For participants with Gilbert's syndrome: No change in baseline TBL	None	
 • No Action
	If normal at baseline: ALT > 5 x ULN for more than two weeks If elevated at baseline: ALT > 3 x baseline AND >5x ULN for more than two weeks or ALT ≥5x baseline AND ≥8x ULN	Normal For participants with Gilbert's syndrome: No change in baseline TBL	None	
 • Interrupt study treatment • Measure ALT, AST, ALP, GGT, TBIL, INR, albumin, CK, and GLDH in 48-72 hours. • Follow-up for symptoms. • Initiate close monitoring

	ALT	TBL	Liver Symptoms	Action
	If normal at baseline: ALT > 8 x ULN	Normal	None	and workup for competing etiologies.
ALT increase with bilirubin increase:				
	If normal at baseline: ALT > 3 x ULN	TBL > 2 x ULN (or INR > 1.5) For participants with Gilbert's syndrome: Doubling of direct bilirubin	None	
 Study treatment can be restarted only if another etiology is identified and liver enzymes return to baseline.
	If elevated at baseline: ALT > 2 x baseline AND >3x ULN			
	If normal at baseline: ALT > 3 x ULN	Normal or elevated	Severe fatigue, nausea, vomiting, right upper quadrant pain*	
	If elevated at baseline: ALT > 2 x baseline AND >3x ULN			

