10.6.1 Specific Renal Alert Criteria and Actions and Event Follow-up

Table 10-4 Specific renal alert criteria and actions

Renal Event	Actions
eGFR decrease 25-49%	
 • Consider causes and possible interventions • Repeat laboratory values within 48 hours of receipt of abnormal test results. Assess patient for signs and symptoms of illness, AKI, etc.
eGFR decrease $\geq 50\%$ * OR if <18 years old, eGFR < 35 mL/min/1.73 m ²	
 • Consider causes and possible interventions • Repeat assessment within 24-48 hours if possible • Repeat laboratory values within 48 hours of receipt of abnormal test results. Assess patient for signs and symptoms of illness, AKI, etc. • Consider drug interruption or discontinuation unless other causes are diagnosed and corrected • Consider referral to nephrologist for diagnosis and management • Consider patient hospitalization and specialized treatment
New onset dipstick proteinuria $\geq 3+$ OR PCR ≥ 1 g/g Cr	
 • Confirm presence of true proteinuria by quantification: protein-creatinine on first morning void • Consider causes and possible interventions • Assess serum albumin & serum total protein

Renal Event	Actions
New onset hematuria \geq 3+ on urine dipstick	
 • Repeat assessment to confirm • Consider drug interruption or discontinuation unless other causes are diagnosed and corrected • Consider referral to a nephrologist • Obtain urine microscopy to distinguish hemoglobinuria or myoglobinuria from hematuria • Assess sCr • Exclude infection, trauma, calculi, bleeding from the distal urinary tract/bladder, menstruation • Consider bleeding disorder

* Corresponds to KDIGO criteria for Acute Kidney Injury

Table 10-5 Renal Event Follow-Up

FOLLOW-UP OF RENAL EVENTS

Monitor patient regularly (frequency dependent on clinical course and consultant advisement) until -

- Event resolution: sCr within 10% of baseline or PCR < 1 g/g Cr, or ACR <300 mg/g Cr, or
- Event stabilization: sCr level with \pm 10% variability over last 6 months or PCR stabilization at a new level with \pm 50% variability over last 6 months.

Analysis of urine renal markers in samples collected over the course of the DIN event

11 References

References are available upon request

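### Section 6.5 bans every interruption, but the liver tables direct it and other sections allow it; the estimand covers the result only in part

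*Protocol*

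**What the plan says.** Protocol Section 6.5 is a single sentence: "Investigational or other study treatment dose adjustments and/or interruptions are not permitted". The summary (Section 1.1, Treatment Groups) agrees: "Investigational study treatment dose adjustments and/or interruptions are not permitted". Neither refers to an exception elsewhere.

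Other sections read differently:

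- **Liver.** Table 10-2 gives the action "Interrupt study treatment" for defined ALT patterns, followed by "Study treatment can be restarted only if another etiology is identified and liver enzymes return to baseline". Table 10-3 puts interruption among the required actions for isolated bilirubin above 3 and up to 10 times the upper limit. The text of Section 10.5 asks sites to consider interruption after a confirmed elevation. Section 7.1 sends sites to this appendix and to the renal one.
- **Renal.** Table 10-4: "Consider drug interruption or discontinuation unless other causes are diagnosed and corrected".
- **Overdose.** Under Section 6.7 the investigator and medical monitor determine "whether study treatment should be interrupted or whether the dose should be reduced".
- **Prohibited medication.** Section 6.8.2 says that taking such a drug "may require the participant to be withdrawn or DFV890 treatment to be put on hold". Table 6-7 lists one action for every class, discontinuation. Section 7.1 makes prohibited treatment a ground for required discontinuation, by reference to the prohibited-treatment section.

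In Protocol Table 3-2 and SAP Table 1-2, permanent discontinuation removes all later data. The row for "Unforeseen use of medication expected to have a limited effect on the primary endpoints (i.e., any other prohibited medications") removes only the next assessment. Two nonadherence rows (DFV890 only) also remove the next assessment: one for more than 20% of daily doses missed over 3 weeks, one for any dose missed in the final 2 days. The SAP adds treatment lasting under 17 days. SAP Section 5.5 adds deviation codes TRT01 and TRT02 (treatment deviations affecting PD) and TRT05 to TRT08 (compliance bands). No row names interruption, hold, dose reduction or restart.

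**The concern.** A site that meets a liver trigger has two instructions that cannot both be obeyed. Following Table 10-2 breaches Section 6.5, and following Section 6.5 ignores Table 10-2. Sites may resolve this differently.

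The analysis inherits the ambiguity. DFV890 is up-titrated over four fixed dosing periods, and each end-of-period value enters the model at its dose. Whether a participant is stopped, held or given less drug decides which of those values are used. If the plan does not settle this, it falls to case-by-case deviation review under SAP Section 2.2. Protocol Section 6.3.2 lets the study statistician see the randomization list at any time, so that review is not necessarily blinded.

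**Working it through.** The plan gives no figure to reproduce. The check compares the texts, then applies the estimand's own rules.

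**1. Force of each text against Section 6.5**

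| Source | What it does | Compatible with a full ban? |
|---|---|---|
| Tables 10-2, 10-3 | Direct interruption; Table 10-2 allows conditional restart | No |
| Section 6.8.2 | A hold is one possible outcome, after discussion with the sponsor | Only if the hold is never used |
| Section 10.5 text, Table 10-4 | Ask for interruption to be considered | Yes, if it is considered and not done |
| Section 6.7 | Leaves interruption or reduction to be decided | Yes, if neither is chosen |

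Only the liver tables are irreconcilable as written. The others offer an option that Section 6.5 removes.

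**2. Prohibited medication: end-of-period assessments lost**

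Take a drug in the limited-effect class, started in dosing period *k* of 4, in a participant who is otherwise complete. After discontinuation, the assessments for periods *k* to 4 go: 5 − *k*. After a hold confined to that period, only the next one goes: 1.

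| Period of event | Discontinued (5 − *k*) | Held and restarted |
|---|---|---|
| 1 | 4 | 1 |
| 2 | 3 | 1 |
| 3 | 2 | 1 |
| 4 | 1 | 1 |

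The SAP keeps an end-of-treatment visit made within 1 day of the last dose after at least 17 days in the period. That does not alter the count, because the medication row already excludes that visit as the next assessment.

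**3. What the nonadherence rows catch, if held doses count as missed**

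Three weeks is 21 daily doses, and 0.2 × 21 = 4.2. Five missed doses (5/21 = 23.8%) exceed 20%; four (4/21 = 19.0%) do not. One continuous gap of *L* days has 22 − *L* possible positions. For *L* up to 4, it escapes both rows if it ends by day 19, which gives 20 − *L* positions.

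| Gap (days) | Positions | Assessment retained |
|---|---|---|
| 1 | 21 | 19 |
| 2 | 20 | 18 |
| 3 | 19 | 17 |
| 4 | 18 | 16 |
| 5 or more | 22 − *L* | 0 |

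Table 10-2 asks for repeat tests at 48–72 hours. A gap of that length is 2–3 doses, or 2/21 = 9.5% to 3/21 = 14.3%, and is usually retained. This is an illustration: restart depends on cause and recovery, and no duration is stated. If the denominator were a 17- or 19-day period (an assumption; the tables say 3 weeks), 20% would be 3.4 or 3.8 doses and the threshold would be 4.

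SAP Section 2.4.1 computes treatment duration as last date minus first date plus 1. If the 17-day test uses that definition, a mid-period gap does not shorten it.

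**4. What remains open**

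The table in step 3 depends on its premise. Protocol Section 6.2.3 defines a missed dose as a full dose not taken within 12 hours of the usual time. Read literally, that includes a held dose. But it sits in the dosing instructions to participants, and neither estimand table refers to it. If held doses do not count, the missed-dose rows exclude nothing after a hold of any length. For a reduced dose, no rule says whether the period enters the Emax model at the assigned dose, at the dose taken, or not at all.

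**The case against.** The strongest reply is that the estimand already deals with interruption. A gap in daily dosing is a run of missed doses. On that footing every gap of 5 days or more is excluded, as is any shorter gap touching the last 2 days. A permanent stop has its own row, the deviation codes add session-level exclusions, and SAP Section 2.5.6 provides an analysis with no intercurrent-event exclusions. This largely stands. A reader might infer that the estimand has no rule, or that nothing says which assessments stay; the documents do not support that. What is missing is a statement that an investigator-directed hold counts as missed doses, and a rule for reduced doses.

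The second reply is that the conflicts differ in force. This also stands: it would be wrong to say that every one of these sections is impossible to follow alongside Section 6.5.

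Third, a reader might infer that safety action would be delayed. Section 10.1.8.1 expects immediate action for participant safety even where it deviates from the protocol, and Section 8 asks for prompt discussion with the sponsor. That answers the concern about delay but not the contradiction, since following Table 10-2 would then count as a deviation.

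Fourth, the limited-effect row might be read as presuming that treatment continues. It says only which assessment is dropped, and the discontinuation row can apply as well.

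Finally, it is tempting to express one lost participant as a share of those reaching 100 mg. No interruption rate is given, and the 100 mg estimate comes from a model using all doses, so that share would not measure expected loss.

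**Conclusion.** The point holds as an internal inconsistency with a limited consequence for the analysis. The conflict between Section 6.5 with the summary and Tables 10-2 and 10-3 is direct. The conflict between Section 6.8.2 and Table 6-7 is real and changes the primary dataset: up to four end-of-period assessments lost against one, for an event in period 1, assuming the drug is in the limited-effect class and the hold stays within the period. The renal and overdose texts are looser mismatches.

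The estimand's coverage is partial. If held doses count as missed, only gaps of 1 to 4 days that avoid the last 2 days of a 21-day window are retained. Whether they count is unstated, and reduced-dose periods have no explicit rule. No sample size, power or error-rate figure changes, and how often interruptions would occur cannot be judged from the documents.

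**What to change.** The sponsor should reconcile Section 6.5 and the summary with Sections 6.7, 6.8.2, 7.1 and 10.5 and Tables 6-7, 10-2, 10-3 and 10-4, so that each event leads to one instruction. Which clinical rule is right is for the sponsor to decide; this review takes no position.

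If interruption or dose reduction remains possible, add to Protocol Table 3-2 and SAP Table 1-2:

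- whether doses withheld on the investigator's instruction count as missed under the nonadherence rows;
- how a reduced-dose period is treated in the Emax model, including the dose it carries if kept.

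If the ban is kept throughout, these additions are unnecessary, but the conflicting text must change.

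The cost is wording. Section 10.1.8.1 requires a written amendment for any protocol change, and the SAP needs matching text in one table. No new data or visits are needed.

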6.6 Continued access to study treatment after the end of the study

Investigational drug will not be provided to participants following the end of the study.

6.6.1 Post trial access

Not applicable.

6.7 Treatment of overdose

In the event of an overdose, the Investigator/treating physician should:

- Contact the medical monitor immediately.
- Evaluate the participant to determine, in consultation with the medical monitor, whether study treatment should be interrupted or whether the dose should be reduced.
- Closely monitor the participant for any AE/SAE and laboratory abnormalities until DFV890 can no longer be detected systemically (at least 7 days).
- Obtain a plasma sample for PK analysis within 7-10 days from the date of the last dose of study treatment if requested by the medical monitor (determined on a case-by-case basis).
- Document the quantity of the excess dose as well as the duration of the overdose.

6.7.1 Reporting of study treatment errors including misuse/abuse

Medication errors are unintentional errors in the prescribing, dispensing, administration or monitoring of a medicine while under the control of a healthcare professional, participant or consumer (EMA definition).

Misuse refers to situations where the medicinal product is intentionally and inappropriately used not in accordance with the protocol.

Abuse corresponds to the persistent or sporadic, intentional excessive use of a medicinal product, which is accompanied by harmful physical or psychological effects.

Study treatment errors and uses outside of what is foreseen in the protocol will be recorded on the appropriate CRF irrespective of whether or not associated with an AE/SAE. Study treatment errors and uses outside of what is foreseen in the protocol, misuse or abuse will be collected and reported in the safety database irrespective of it being associated with an AE/SAE within 24 hours of Investigator's awareness. For more information on AE and SAE definition and reporting requirements, please see the respective sections.

6.8 Concomitant and other therapy

6.8.1 Concomitant therapy

All medications, procedures, and significant non-drug therapies (including physical therapy and blood transfusions) administered after the participant was enrolled into the study must be recorded on the appropriate CRFs.

Each concomitant drug must be individually assessed against all exclusion criteria and prohibited medication. If in doubt, the Investigator should contact the Novartis medical monitor before randomizing a participant or allowing a new medication to be started. If the participant is already enrolled, contact Novartis to determine if the participant should continue participation in the study.

